1. PURPOSE OF STUDY

1.1. Overall Goal:

We have developed a Discussion Prioritization Tool (DPT) for older adults considering adjuvant chemotherapy. The DPT utilizes Conjoint Analysis (CA) methodology and the objective of the current study is to assess usability of this DPT in our target population, older adults with breast cancer and to adapt the tool to optimize usability for our target population.

1.2. Study objectives and Hypothesis:

1.2.1. Primary objective:

To evaluate the usability of the DPT in ten older adults considering adjuvant chemotherapy or has made a decision about receiving adjuvant chemotherapy for breast cancer within the past 12 months.

1.2.2. Secondary objective:

To adapt the DPT using “talk aloud” method to optimize usability for our target population.

1.2.3. Hypothesis:

The DPT tool will demonstrate adequate usability in older adults considering adjuvant chemotherapy or has made a decision about receiving adjuvant chemotherapy for breast cancer within the past 12 months.

1.2.4 Usability and feasibility metrics:

The usability and feasibility of the DPT will be evaluated based on the following:

Primary Usability Assessment Measures: System Usability Scale (SUS) (score on 10-item scale, total score ranging 0-100; higher score corresponds to greater usability). We will deem the tool usable if our mean SUS score among the 10 patients enrolled is >68.

Secondary Usability Assessment Measures:

- a) Recruitment rates (percentage of patients who are approached and agree to enroll)
- b) Talk Aloud Method (recordings of patients feedback while using the DPT)

2. BACKGROUND AND RATIONALE

2.1 Breast Cancer is a disease of aging. Among other elements, age is a crucial risk factor in developing cancers. In breast cancer specifically, incidence has been shown to rise with age, resulting in the majority of deaths related to breast cancer occurring in women aged 65 years and older [1]. In 2016, it was found that the prevalence of breast cancer among women aged 65 and over was 436.9 per 100,000 per year [2]. In patients with breast cancer, many are considered for adjuvant systemic therapy (e.g. chemotherapy). This is particularly relevant for older adults with higher risk breast cancer subtypes. For example, nearly 15% of older patients have triple negative breast cancers, which represent the most aggressive breast cancers with the majority of recurrences occurring within the first several years after treatment [1].

2.2 Patient goals and preferences are an important component in developing treatment plans for localized breast cancer. Providing patient-centered care that incorporates patient goals and values in the oncology treatment decision making process is important [1]. When it comes to healthcare decisions, each patient has their own individual goals, beliefs, preferences, life experiences and values that influence their treatment preferences [1]. Identifying what is important to patients with breast cancer can ultimately tailor conversations for each patient when discussing cancer treatment options. In addition, evaluating the patient's overall health and potential risks and benefits of various treatment option is also critical, particularly for older adults. The geriatric assessment (GA) is a validated tool to assess the overall health status of older adults and is superior to other measures of "fitness" in oncology (e.g. performance status assessment) [3]. The GA is a multidimensional tool that assesses domains relevant for older adults, including comorbidities, psychological status, functional status, physical performance, cognition, nutritional status, social support and polypharmacy and is recommended by national guidelines in the care of older adults with cancer [3]. Awareness of potential deficits or vulnerabilities in these areas (through the completion of the GA) could ultimately assist in decision making or can be used to identify patients who would benefit from interventions that would improve their health for treatment [3].

2.3 Information preferences vary amongst older adults with breast cancer. When deciding about treatment options, patients were shown to have three different styles such as physician based, patient based, or shared. Patients who made decisions based on their physicians, did so in fear of making the wrong choice. Other patients were satisfied making their own choices, while others relied on support from their physician to help make a shared decision about treatment [4]. Some patients elect to decline adjuvant therapy, and studies suggest a variety of reasons for this including prior family experience, not wanting to burden others, clinical comorbidities that could increase their chance of adverse effects, and prior negative experiences [4]. Overall, there are multiple key elements that a patient considers when making decisions about treatment.

2.4. The aging process is heterogeneous and older adults of a similar chronologic age do not necessarily have similar health status. A geriatric assessment (GA) can be utilized to better understand the overall health status of an older adult. GA has been shown to be feasible in oncology[5] and also improves communication about aging-related issues between older adults with cancer and their oncologists.[6] Elements of the GA are associated with chemotherapy toxicity and other adverse outcomes such as hospitalization and early termination of chemotherapy. Recently, a risk model was developed and validated for older adults receiving adjuvant therapy for breast cancer (the Cancer and Aging Research Group-Breast Cancer [CARG-BC]) to estimate the risk of chemotherapy toxicity and other adverse events.[7] The CARG-BC includes clinical variables (e.g. cancer stage), laboratory results (e.g. liver function test), as well as GA elements (e.g. fall history) and a total sum score is calculated. The total CARG-BC score correlates with a risk of chemotherapy toxicity. Providing the results of a patient's GA, their CARG-BC score, and their preferences about treatment options may facilitate a more personalized discussion about the benefits and risks of adjuvant treatment options for older adults with breast cancer.

2.5. Conjoint analysis is a method for eliciting patient preferences. Given the complexity of adjuvant chemotherapy decision making for older adults with breast cancer, enhancing support and promoting treatment discussions in the context of patient's goals and preferences is an important need. With this need in mind, our group has completed interviews with patients with cancer patients who are considering adjuvant therapy. As a result of these interviews, our group has developed a common list of attributes (variables found to be important in decision making)

that were used to create the Discussion Prioritization Tool (DPT) using Conjoint Analysis (CA) methodology. CA which is a method that can assess the relative importance that patients place on different aspects of care by asking patients to make a series of trade-offs between competing options. Attributes that were identified were quality of life, fatigue, activities of daily living, falls/balance, cognition, distress/worry, risk of treatment toxicity, risk of hospitalization, burden on support system, and outcome (recurrence risk/survival) [8].

Other decisional support tools have been developed and tested in oncology and demonstrated promising utility. For example, CONNECT, a computer-based communication aid, was developed to improve communication between patients with advanced cancer and their oncologists.[9] CONNECT included assessment of patient values, goals, and communication preferences and was tested in a 3-arm, prospective, randomized clinical trial. Patients who engaged with the CONNECT tool felt that it made treatment decisions easier to reach and helped them to be more satisfied with these decisions. Patients in the intervention arms also reported higher levels of satisfaction with communication. Other decision aids have also shown potential benefit, but the majority of these focused on patients with advanced cancer[10-13] or were not specific for the older adult population.[14, 15] To our knowledge, this is the first discussion prioritization tool developed for older adults with breast cancer considering adjuvant chemotherapy that incorporates GA and aging-specific preferences and relates patient preferences to validated risk tool results (the CARG-BC).

3. ADMINISTRATIVE ORGANIZATION

3.1. Research location and participating site:

The study will be conducted through the Wilmot Cancer Institute at the University of Rochester Medical Center and will enroll patients through the Comprehensive Breast Care Center (located at Pluta Cancer Center)

[name], of the City of Hope is a co-investigator on the protocol. However, we will not be enrolling patients from the City of Hope. [name] will only have access to de-identified data and will be participating in data analysis for this study.

4. STUDY DESIGN

4.1 Study Design:

This is a single arm pilot study to determine usability.

5. SUBJECT POPULATION

5.1 Subject Population:

The eligibility criteria is aimed at identifying older patients diagnosed with localized breast cancer who are being considered for adjuvant chemotherapy or has made a decision about receiving adjuvant chemotherapy for breast cancer within the past 12 months. Since our study team is developing a tool that incorporates geriatric specific factors, we will recruit patients who are aged 65 or older. The study will have no restrictions on race or gender. However due to the disease, we anticipate that most, if not all participants will be female.

5.2 Number of subjects:

Our study team expects 10 subjects to participate in the study. The majority of usability studies demonstrate that usability can be optimized in a small number of subjects (e.g. 10). We anticipate being able to enroll the targeted number of patients in <1 year duration.

5.3 Vulnerable Subjects:

Recruitment will exclude vulnerable populations such as fetuses, neonates, children, pregnant woman, prisoners, adults with decisional impairment, and institutionalized individuals.

6. INCLUSION AND EXCLUSION CRITERIA

6.1 Inclusion Criteria.

- Age ≥ 65
- Diagnosis of stage I-III BC
- Being considered for adjuvant chemotherapy or has made a decision about receiving adjuvant chemotherapy for breast cancer within the past 12 months.
- Able to speak and read English
- Able to participate in study procedures.

6.2 Exclusion Criteria.

- Lacking medical decision-making capacity as determined by their oncologist
- Evidence of metastatic disease

7. RECRUITMENT AND CONSENT

Subjects will be identified and enrolled at the University of Rochester Comprehensive Breast Cancer Center at Pluta Cancer Center. The clinic schedules of breast oncologists and their advanced practice providers (APPs) will be screened for eligible patients.

To ensure appropriate safety precautions when conducting in-person study procedures, the process for conducting in-person visits outlined in the Guidance for Human Subject Research will be followed.

7.1 Identification of Study Subjects, Recruitment, and Consent Procedures

Potential patients will be identified in multiple ways. First, study participants will be identified by their treating physician, the nurses that work with the physicians, and the study coordinator. The study coordinator works closely with the physicians and nurses to monitor patients and identify those patients who are being considered for adjuvant chemotherapy or has made a decision about receiving adjuvant chemotherapy for breast cancer within the past 12 months. With permission from oncology providers, we will screen for eligible patients from clinic schedules. The study coordinator contacts the physician (or their designee) and lets them know that a patient may be eligible for the study. The physician (or their designee) then confirms if the patient is a good study candidate or not and affirms that the patient has decision making capacity. If there is a question about eligibility, the principal investigator will be contacted and will meet with the patient and/or health care proxies, review the medical records, and perform an assessment of eligibility if necessary. After meeting with the physician (or their designee), the study coordinator will meet with the patient either in person or via phone, and explain the details of the study. Study staff will introduce the study to the patients and provide adequate

time to read the consent.

Our study group anticipates two different types of scenarios for the recruitment and consent process. Potential study subjects may be consented either in person or verbally during a virtual visit. Study participants will also have the ability to complete the study in person or virtually.

Potential scenarios for in-person consent:

- 1) Physician/Study Investigator makes the initial contact and provides consent form, and patient signs consent with the physician on the same day: After confirming with the physician (or their designee) that a patient is a potential candidate for the study, the study staff will provide a consent form to the treating physician/study investigator so he/she can provide it to the patient during an in-person clinic visit. The physician/study investigator will go over every detail of the study during the clinic visit with patient. If agrees, the patient will sign the consent form with the physician/study investigator during the same in-person visit.
- 2) Study staff makes the initial contact and provides consent form, and patient signs consent with the study staff on the same day: After confirming with the physician (or their designee) that a patient is willing to speak with the study coordinator about the study, the patient will be provided with an informed consent form by the study staff when they come in for an in-person clinic visit. The study staff will introduce the study to the patients and go over every detail of the study. If agrees, the patient will sign the consent form with the study staff during the same in-person visit with the study staff.

Potential scenarios for verbal consent:

- 1) Physician/Study Investigator makes the initial contact, study staff follows up with the patient on the phone, and patient provides verbal consent on the phone: After confirming with the physician (or their designee) that a patient is a potential candidate for the study, the physician/study investigator confirms with the patient that he/she is willing to speak with the study staff about the study. The study staff will then call the patient via phone. The study coordinator will use the verbal consent script as a written aid and will go over every detail of the study with the patient to recruit them for the study. Study staff will sign and date it to confirm that he/she followed the script and the patient agrees to participate in the study. Following the completion of verbal consent with the subject, the coordinator will mail or email the subject a study information sheet that summarizes what the study entails and the subject's involvement in it.
- 2) Physician/Study Investigator makes the initial contact and provides consent form, study staff follows up with the patient on the phone, and patient provides verbal consent on the phone: After confirming with the physician (or their designee) that a patient is a potential candidate for the study, the study staff will provide a consent form to the treating physician/study investigator so he/she can provide it to the patient during an in-person clinic visit. If the patient is interested but does not want to consent on the same day, the patient will bring the consent form home. The study staff will then call the patient via phone. The study coordinator will use the verbal consent script as a written aid and will go over every detail of the study with the patient to recruit them for the study. Study staff will sign and date it to confirm that he/she followed the script and the patient agrees to participate in the study. Following the completion of verbal consent with the subject, the

coordinator will mail or email the subject a study information sheet that summarizes what the study entails and the subject's involvement in it.

- 3) Study staff makes the initial contact and provides consent form, study staff follows up with the patient on the phone, and patient provides verbal consent on the phone: After confirming with the physician (or their designee) that a patient is willing to speak with the study coordinator about the study, the patient will be provided with an informed consent form by the study staff when they come in for an in-person clinic visit. If the patient is interested but does not want to consent on the same day, the patient will bring the consent form home. The study staff will then call the patient via phone. The study coordinator will use the verbal consent script as a written aid and will go over every detail of the study with the patient to recruit them for the study. Study staff will sign and date it to confirm that he/she followed the script and the patient agrees to participate in the study. Following the completion of verbal consent with the subject, the coordinator will mail or email the subject a study information sheet that summarizes what the study entails and the subject's involvement in it.

7.1.1. Informed Consent

Informed consent will be obtained from the patient by the study investigators or coordinators. Consent documents will be signed by the patient and maintained in the patient record with copies provided to the patient. For verbal consent, documents will be maintained in the patient record with copies provided to the patient. Justification for waiver of documentation of written consent: If the patient cannot meet in person with the study coordinator to sign the informed consent, the study coordinator will verbally consent the subject. The study coordinator will use the verbal consent script, then sign and date it to confirm that s/he followed the script and the subject agreed to participate in the study. Following the completion of verbal consent with the subject, the coordinator will mail or email the subject a study information sheet that summarizes what the study entails and the subject's involvement in it.

Alteration of HIPAA Authorization:

We are requesting an altering of HIPAA authorization. We will provide an information sheet to patients who provided verbal consent. Verbal consent will allow for reduction of in-person visits, thus maximizing the safety of both patients and study staff. Nonetheless, when possible and if we are able to coordinate study and clinic visits, we will obtain written informed consent.

The study cannot be conducted without the use of protected health information (PHI) as we have to link patient reported data with medical history collected on electronic medical record. We have adequate plans to protect the PHI from improper use and disclosure. We will destroy identifiers after completion of the study for 7 years. We will not reuse or disclose the PHI to another person or entity other than the study investigators. The waiver will not adversely affect the privacy rights of the individual and the research cannot be practicably done without access to the use of the PHI.

7.1.2. Human Subject Protection

The University of Rochester Research Subject Review Board Investigator Guidance policy

will be used to ensure that ethical standards for human subjects are upheld.

7.1.3. Participation

Regulations at the state, federal, and institutional level will be adhered to in regards to informed consent. Study participation is completely voluntary. After consenting, participants may withdraw from the study at any time for any reason, and they may do so without any repercussions. Participants may also be withdrawn by study personnel if it is determined that it is not favorable for the patient. All information regarding consent and withdrawal will be kept confidential.

7.1.4. Duration

Participation in the study will last approximately 60-90 minutes during a one time in-person or virtual visit. If needed, our study team may follow up with the participant for further information for up to 2 months after the initial completion of the study procedures. After the study is completed, participant data will be maintained for 7 years at URMC and will be kept in a password-protected database.

7.1.5 Subject Capacity

We will ensure through the patient's primary oncologists that the patient has capacity to consent and participate in the study by confirming the patient's medical decision-making capacity with the oncologist.

7.1.6 Subject/Representative Comprehension

The study subject's capacity to participate in the study will be confirmed by their primary oncologist prior to approaching the patient to discuss the study. During the consent process, the subject must be able understand and report the purpose of the study, its procedures, risks, and benefits in order to demonstrate full comprehension of the study.

8. REGISTRATION

If a patient meets eligibility criteria and has provided informed consent, the study personnel will enter the following information into the OnCore Database:

8.1. Registration Information

- 8.1.1** Site
- 8.1.2** Most recent IRB approval date
- 8.1.3** Name of person registering study participant
- 8.1.4** Eligibility verification

- 8.1.5** Verification that consent form has been signed and date signed. If verbal consent obtained, verification that verbal consent form has been signed and dated by the consenting individual.
- 8.1.6** Treatment facility (Pluta)
- 8.1.7** Participant's identification
 - 8.1.7.a** First and last names
 - 8.1.7.b** Birth date (MM/DD/STREAM)
 - 8.1.7.c** Gender
 - 8.1.7.d** Race
 - 8.1.7.e** Five-digit zip code
 - 8.1.7.f** Medical Record Number
 - 8.1.7.g** Ethnicity
 - 8.1.7.h** Patient's preferred and alternate phone numbers (and email address if patients consent to be contacted via email)
 - 8.1.7.i** Date of baseline visit

9.0. DISCUSSION PRIORITIZATION TOOL

The proposed tool consists of three components:

- 1) A survey tool consisting of demographic questions and selected patient-reported Geriatric Assessment measures;
- 2) Selected coordinator-administered geriatric assessment measures; and
- 3) The Conjoint analysis to elicit patient preferences, (see Figure 1 for depiction of conjoint analysis question).

- 9.1 Demographic measures (see table 1.a)
- 9.2 Patient-reported GA measures (see table 1.b)
- 9.3 Coordinator-administered GA measures (see table 1.c)
- 9.4 Conjoint Analysis

There are two main components of a conjoint analysis i.e., attributes (characteristics or factors that influence decision-making) and levels (degree of the characteristics). These attributes are categorized into 3 separate groups: benefits of treatment, potential risks of treatment, and quality of life during treatment. Scenarios are then drawn up for each of the attributes and levels (Figure 1). Patients will be presented with scenarios and asked to select one that is consistent with their preferences. This process then repeats until all attributes are evaluated. At completion, a summary containing a ranking of factors will be provided to the oncologists. A summary with patient concerns (i.e., factors that are important to them) and question prompt list will be provided to patients.

Table 1 outlines the attributes that are included in the conjoint analysis. Attributes are organized by Meta-Attributes (global descriptors of how attributes are organized). The software presents one attribute in each of the 4 meta-attributes for each hypothetical scenario (see figure 1 for layout of how met-attributes are presented; see table 1 for attributes in each meta-attribute).

Table 1: List of Meta-Attributes and Attributes included in the conjoint analysis.

Meta-Attribute	Attribute
Benefit of Therapy	Recurrence Risk
	Survival
	Worry/distress
Side Effects of Therapy	Fatigue
	Falls/Balance
	Cognition
	Risk of treatment Toxicity
Hardship	Risk of hospitalization
	Burden on support system
Quality of life	Relatively unchanged
	Significantly worse than it is right now

[figure not shown]
Figure 1 below is a representation of how the conjoint scenarios are displayed. This is an iterative process, whereby participants select one hypothetical scenario from the first set of options. They subsequently are presented with a second set of options and are asked to again select a preferred hypothetical scenario. Figure 1 is an image of how the scenarios appear to participants when using the online tool.

Figure 1:

Treatment 1	Treatment 2	Treatment 3
The treatment would:	The treatment would:	The treatment would:
		
Decrease my worry about the cancer	Decrease my worry about the cancer	Increase the number of years that I am likely to live
But the treatment may also cause me to:	But the treatment may also cause me to:	But the treatment may also cause me to:
		
Feel more tired and limit my day-to-day activities	Have changes in my thinking that limit my day-to-day abilities	Have changes in my thinking that limit my day-to-day abilities
and	and	and
		
Need more help from others for day-to-day activities	Be hospitalized due to side effects	Be hospitalized due to side effects
During the treatment my Quality of Life would be:	During the treatment my Quality of Life would be:	During the treatment my Quality of Life would be:
		
Relatively unchanged	Significantly worse than it is right now	Relatively unchanged
		

When participants have completed the exercise, the tool provides output ranking of the meta-attributes and three attributes (benefit of therapy, side effects of therapy, hardship). Figure 2 is an example image of how the output of patient preferences can appear for the meta-attribute and side effects of therapy.

Figure 2: Conjoint analysis output example of meta-attribute and attribute ranking.

As described below in study procedures, results of the conjoint analysis as well as geriatric assessment results are provided to participants. For oncologists, the results provided include the conjoint analysis output, geriatric assessment results, and CARG-BC score.

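### Does leaving activities of daily living out of the conjoint item list (Section 9.4, Table 1) require a change to the tool or the plan?

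*Combined protocol and SAP*

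**What the plan says.** Section 2.5 describes a list of attributes drawn from patient interviews, "that were used to create the Discussion Prioritization Tool (DPT"). The list begins: "Attributes that were identified were quality of life, fatigue, activities of daily living, falls/balance, cognition". It goes on to distress or worry, treatment toxicity, hospitalization, burden on the support system, and outcome (recurrence risk and survival). The same section presents the tool as one "that incorporates GA and aging-specific preferences".

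In Section 9.4, "Table 1 outlines the attributes that are included in the conjoint analysis". Its rows fall under four meta-attributes:

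- Benefit of Therapy: recurrence risk, survival, worry/distress.
- Side Effects of Therapy: fatigue, falls/balance, cognition, treatment toxicity.
- Hardship: hospitalization, burden on the support system.
- Quality of life: two levels.

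Figure 1 shows the participant's screen. Three of its statements refer to daily function: "Feel more tired and limit my day-to-day activities", "Have changes in my thinking that limit my day-to-day abilities" and "Need more help from others for day-to-day activities". On completion, "the tool provides output ranking of the meta-attributes and three attributes (benefit of therapy, side effects of therapy, hardship"). Participants and oncologists receive these results together with the geriatric assessment results.

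**The concern.** An attribute that patients raised in interviews, and that the protocol says helped to build the tool, is missing from the list of items the tool can rank. Its content is spread over three items in two groups, so the ranks of fatigue, cognition and burden each mix a symptom or circumstance with its effect on daily life. A patient whose chief worry is keeping up daily activities would see those three items in the ranking and no ADL line.

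The ranking goes to participants and oncologists, some participants are still considering chemotherapy, and the tool is to be carried into a randomized trial about the content of conversations. If the omission were an oversight, the pilot would be the cheap place to catch it. The self-reported instrumental ADL (IADL) measure in the geriatric assessment does not fill the gap, because it records current function and not how much the patient values keeping it.

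**Working it through.** The documents give no figure to reproduce, and no error rate or sample size is involved. The check is a comparison of lists, followed by a test of whether the size of the problem can be stated.

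**1. Section 2.5 against Table 1 of Section 9.4.** Section 2.5 gives 10 attributes, counting outcome as one.

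| Section 2.5 | Table 1, Section 9.4 |
|---|---|
| Quality of life | Meta-attribute with two levels |
| Fatigue | Side Effects |
| Activities of daily living | No row |
| Falls/balance | Side Effects |
| Cognition | Side Effects |
| Distress/worry | Benefit |
| Treatment toxicity | Side Effects |
| Hospitalization | Hardship |
| Burden on support system | Hardship |
| Outcome | Benefit, split into recurrence and survival |

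Nine of ten map, and ADL does not. The three ranked groups hold 3 + 4 + 2 = 9 items.

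**2. Figure 1.** Four distinct harm statements are visible. Three mention day-to-day activities or abilities: 2 of 2 under Side Effects and 1 of 2 under Hardship. The wording for falls/balance and toxicity is not shown, so three is a minimum.

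**3. Can the current items separate ADL?** Write each item's utility as a sum of parts, with t for tiredness, c for thinking changes, h for needing help and d for loss of daily activity. Then

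- u(fatigue) = t + d
- u(cognition) = c + d
- u(burden) = h + d

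Patient A has d = -1 and the rest 0. Patient B has t = c = h = -1 and d = 0. Both have utility -1 on all three items, so their choices must agree. The tool allows 3 × 4 × 2 × 2 = 48 profiles and 48 × 47 × 46 / 6 = 17,296 three-option sets, and A and B differ in 0 of them. The zero follows from how A and B were defined. It shows that ADL is not separately identified. It does not show how many patients are affected.

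**4. Would a separate item change the answers by a known amount?** Suppose ADL becomes its own item and the day-to-day wording leaves the other three. The table counts sets in which A's and B's best options differ, ties included, and the share in which they have no best option in common. The first row gives no weight to benefit or quality of life. The weights in the other rows are assumptions.

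| Other weights | ADL under Side Effects (60 profiles, 34,220 sets) | ADL under Hardship (72 profiles, 59,640 sets) |
|---|---|---|
| None | 31,140 differ (91%); none in common 18% | 55,152 differ (92%); none in common 28% |
| Survival 0.5, recurrence 0.2, worse quality of life -0.6 | 21,007 differ (61%); 49% | 39,328 differ (66%); 55% |
| Survival 3.1, recurrence 2.0, worse quality of life -2.6 | 8,731 differ (26%); 11% | 15,664 differ (26%); 13% |

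In the first row at least one patient has tied best options in 96% and 90% of sets, so that row mostly compares tie patterns. Across rows the share that differs runs from 26% to 92%, and the share with none in common from 11% to 55%. The documents give nothing with which to choose a row, and they do not say which sets the software shows. No defensible effect size comes out of this.

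**5. What depends on it.** The primary criterion (Sections 1.2.4 and 17) is a mean SUS score above 68 in 10 patients. The SUS asks about ease of use, complexity and confidence, and none of its ten statements asks which attributes the tool covers.

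**The case for a change.** The strongest case for a change is that the mismatch is real, unexplained and cheap to deal with in a pilot. None of the three closing feedback questions asks about a missing or merged concern, so a participant who says the results do not reflect her preferences may not reveal why. That much stands: the ranking cannot report ADL separately, and the documents do not state whether the merging was intended.

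The rest is weaker.

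- Section 2.5 says the list was used to create the tool. It does not say each attribute becomes a ranked item. Writing daily function into fatigue, cognition and burden is one way of using it.
- The concern is put before the patient. Someone who minds losing daily activities can say so by avoiding those three items, which is a visible functional signal although not a separate one.
- Figure 2, the example output, is not reproduced in the text. If its labels carry the full item wording, the oncologist reads the functional clause as well.
- Talk-aloud runs through both the choices and the review of results, is aimed at problems of function and language (Section 10.1), and is followed by an open request for feedback. Section 17 feeds the themes into the version for the later trial.
- A separate ADL item would mean rewriting three items of a developed tool before the user testing meant to guide such edits. Profiles would rise from 48 to 60 or 72 and free contrasts from 7 to 8, with probably more choice screens for older participants in a 30-60 minute visit.

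**Conclusion.** No change to the plan follows. The facts behind the concern are correct: 1 of 10 interview-derived attributes has no row of its own, and its content sits inside at least 3 of the 6 Side Effects and Hardship items. This is a choice about instrument content that the text leaves unexplained. It is not a flaw in the analysis. Whether ADL should be ranked alone is a fair trade-off between a sharper ranking and a longer exercise, and the study's secondary objective is the place to settle it. The sample size, the SUS criterion and the qualitative analysis are sound if carried out as written.

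Section 9.4 also speaks of three attribute groups in one paragraph and four meta-attributes in the next. That is a clerical slip, since Table 1 plainly shows four. Section 9.4 does not give the formula for the meta-attribute ranking either, but the usability conclusion does not rest on it.

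This conclusion assumes that Figure 1 statements match Table 1 rows by wording and position. It does not depend on the unseen wording of the falls/balance and toxicity items, or on any of the choice-set percentages.
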